Does this protocol/trial require registration on ClinicalTrials.gov due to it: meeting the definition of an Applicable Clinical Trial, being required under the terms and conditions of an award, or being proposed to be published in ICMJE journals?

No, this clinical is not a clinical trial, or does not meet the definition of an Applicable Clinical Trial, or does not need to be registered under the terms and conditions of an award, or is not a clinical trial with results intended to be reported in an journal belonging to the ICMJE. Registration is not required.

Section B: Exempt Request

B. Exempt From IRB Review

Not Applicable

Section C: Background Information

Optimal care and outcomes for persons with dementia (PWD) depend on family caregivers primarily responsible for care coordination and daily care. Behavioral or psychological disturbances are exhibited by 80% of PWD, including 40% who are aggressive. Growing evidence has addressed psychological disturbances of PWD and their caregivers once behavioral problems arise, but examination of prevention of such problems is lacking. Aggressive behaviors are perhaps the most problematic because they lead to increased institutionalization, injuries, caregiver burden and use of antipsychotic medications. Innovative approaches are urgently needed to replace the treatment of aggression with tranquilizing medications because of their associated morbidity and mortality in PWD. We have developed an innovative, behavioral caregiver intervention that aims to prevent development of aggression in at-risk PWD, guided by empirical evidence regarding mutable risk factors for aggression. Our team¿s prior work has identified patient pain and depression, and caregiver/PWD relationship quality as strong predictors of aggression.

Broadening Aggression Prevention Training (APT) to Be More Representative of Target Populations: The veteran sample in our current project is significantly different from the non-VA-using population in several important ways that compel us to test the intervention outside the VA. Almost all (97%) of our currently recruited dyads (n=130) are male Veterans with dementia, with women comprising 95% of the caregiver sample. Our sample is comparable to those of previous studies,

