The objectives of this proposal are to assess whether this caregiver intervention, Aggression Prevention Training for Caregivers of Persons with Dementia (APT), decreases 1) incidence of aggression, 2) aggression-related outcomes(injuries, caregiver burden, nursing-home placement, caregiver burden, positive aspects of caregiving, and behavior problems), and 3) pain and pain-related features (decreased pleasant activity frequency, poor relationship quality, and depressive symptoms).

Secondary objectives are to examine the relationships between executive dysfunction (ED) and 1) pain, 2) caregiver-patient related problems, 3) depression and 4) behavior problems and the association between ED and PWD engagement in the APT intervention.

The proposed study is a randomized, controlled trial of APT, a 6-8 session, home-based intervention. We will recruit 220 community-dwelling dyads (PWD and caregiver) that will be randomized to APT or enhanced usual primary care (EU-PC). APT uses active learning tools, including didactics, role-playing, and multimedia (eg, books and DVDs). Four core modules will address the 4 main aggression risk factors identified by our team and others: a) recognizing pain, b) treating pain pharmacologically and behaviorally, c) increasing pleasant activities to decrease depression, and d) improving the quality of the dyadic relationship through enhanced dyadic communication skills. Caregivers can select 2 to 3 additional elective sessions; the needs of the dyad guide elective selection to further enhance skills related to these core topics. EU-PC provides the patient and caregiver educational materials on pain, notifies the primary care provider of clinically significant pain, depression, and aggression in the PWD (see Reporting and Documentation Procedures attached in Section S), and provides 8 weekly supportive telephone calls to caregivers. PWD and caregiver outcomes will be collected at baseline, and at 3, 6 and 12 months. The CLOX Drawing Test will be administered at baseline to a subset of 100 subjects to measure executive function. Data analysis will include both univariate descriptive statistics and inferential statistics, including regression models, repeated-measure modeling and Cox proportional hazards models.

Section E: Protocol Risks/Subjects

E1. Risk Category

Category 1: Research not involving greater than minimum risk.

E2. Subjects

Gender:

Both

Age:

Adult (18-64 yrs), Geriatric (65+ yrs)

Ethnicity:

All Ethnicities

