We plan to use the information collected on the screening telephone call as research data for the following reasons: 1) We will use the information gathered to determine the reasons potential subjects did not want to participate in the study or did not qualify for the study, to aid in the design of future research targeting this population. 2) Some of the questions asked at screening are also needed to characterize participants that enroll in the study. To reduce study burden, we will not repeat these questions after written informed consent is obtained.

Participants who screen eligible during the telephone assessment and sign consent documents will proceed to baseline. Eligible participants will be randomly assigned to intervention groups (APT or EU-PC) immediately following baseline evaluation based on random numbers generated in SAS PROC PLAN.

Assessments. Assessments will be done at baseline and 3, 6, and 12 months and will consist of a measure of demographic information and validated instruments. They will be administered by independent evaluators (IEs) blinded to random assignment. The CLOX Drawing Test (see Section S) will be administered in-person at baseline to a subset of 100 consecutively enrolled subjects; it should take less than ten minutes to complete. Prior to the assessment, instructions will be given to each subject in terms of what the measure is testing (i.e. ¿I will be assessing your ability to draw a clock¿). The remainder of the assessments will be administered by telephone. An unblinded RA will notify the PCP or referring MD of patients who have been identified as having clinically significant pain, depression, or aggression at baseline or on any of the follow-up calls (see Documentation and Reporting Guidelines attached in Section S).

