In general, the primary source of missing data will be through participant attrition. We anticipate a low attrition rate (10%) based on our prior work. As described below, we will use analytic techniques (eg, hierarchical linear models) that are robust to violation of missing-data assumptions (ie, ¿missing completely at random¿). To reduce the possibility of bias in missing data, where possible, we will incorporate information from secondary sources for participants with missing data from attrition to try to ascertain whether they differ in important ways from other study participants. We will use X2 tests to determine whether there are differences in attrition between the 2 study arms. Prior to testing hypotheses, we will compare baseline demographic and clinical variables in APT and EU-PC with X2 and independent sample t-tests. Variables with p values < .25 in these univariate tests will be included as covariates in all subsequent multivariate models107 or as propensity scores.

Primary Hypothesis: APT will result in lower 1-year incidence of aggression than EU-PC. We will use negative binomial regression models to estimate the difference between our intervention and the control group in the rate of aggressive behavior at the 1-year follow-up period. For participants who drop out of the study, their time until study attrition will be used as their exposure period. Statistical significance will be determined using the X2 statistic associated with the parameter estimate for group membership. Baseline demographic and clinical variables that differ between groups in univariate tests will be included as covariates or propensity scores.

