Secondary Hypotheses 1: APT will result in greater reduction in aggression-related outcomes (nursing home placement, caregiver burden, positive aspects of caregiving, and behavior problems) over the 1-year assessment period than EU-PC. We will separately identify between-group (APT vs. EU-PC) differences in change over the 1-year follow-up period for injuries to PWD or others, caregiver burden, and nursing home placement, using a hierarchical linear modeling approach to repeated-measure modeling. These mixed models will maximize participant data by allowing us to account for various lengths of follow-up for each participant, as well as for missing observations (other than attrition). Conditional models will contain fixed terms for the intercept, treatment group (APT or EU-PC), time period (baseline; 3, 6, or 12 months), treatment group by time period interaction, and any previously identified variables that differ between treatment groups. Modeled random effects will include between-patient variation in baseline scores (i.e., the intercept where baseline assessments are scored 0) and variation in the slopes over time. In other words, we will model and attempt to explain variance between treatment groups for both baseline outcomes and overall change over time in outcomes. Given the 4 time points, the focus will initially be on linear patterns of change, although we will evaluate the relative fit of a quadratic or cubic pattern of change, using the likelihood ratio test. These analyses will allow us to examine the immediate impact of treatment, as well as retention, improvement, or decay in outcomes across the 12-month follow-up period.

Reduction in risk of nursing-home admission will be evaluated using a Cox proportional hazards model to test for between-treatment group differences. Similar to the approach we used for Hypothesis 1 to test for differences in onset of aggression, we will first estimate the unadjusted differences between groups, followed by estimates incorporating all identified covariates.

Secondary Hypothesis 2: APT will result in greater decreases in pain severity and pain-related features (low pleasant-activity levels, poor quality of caregiver-PWD relationship and depressive symptoms) than EU-PC over the 1-year follow-up period. These analyses will be conducted using the same approaches described for secondary Hypothesis 1.

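### The primary model picks covariates by baseline imbalance (p<.25), so the plan's own predictors of aggression usually stay out; the cost is efficiency, and its size depends on inputs the documents do not give

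*Combined protocol and SAP*

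**What the plan says.** Section G1 (Attrition Rates and Missing Data) compares the arms at baseline with chi-square and t tests and then sets the rule for every later multivariable model: "Variables with p values < .25 in these univariate tests will be included as covariates", or else as propensity scores. The Primary Hypothesis paragraph carries this into the negative binomial model: "Baseline demographic and clinical variables that differ between groups in univariate tests will be included as covariates or propensity scores". On exposure it says: "For participants who drop out of the study, their time until study attrition will be used as their exposure period". On the test: "Statistical significance will be determined using the X2 statistic associated with the parameter estimate for group membership". Under Secondary Hypotheses 1, a reference back to Hypothesis 1 describes a two-step approach: "we will first estimate the unadjusted differences between groups, followed by estimates incorporating all identified covariates".

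Section C reports that the team's earlier work "identified patient pain and depression, and caregiver/PWD relationship quality as strong predictors of aggression". Section D lists pain, relationship quality and depressive symptoms among the outcomes, and states: "PWD and caregiver outcomes will be collected at baseline, and at 3, 6 and 12 months". Secondary Hypotheses 3 names the instruments: the Philadelphia Geriatric Pain Intensity Scale, the 30-item Geriatric Depression Scale and the Mutuality Scale.

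Allocation is 1:1 (Section F1) from random numbers (Section F2), with no stratification described. The only covariates fixed in advance are gender and caregiver relationship, in the executive dysfunction regressions. None is fixed for the comparison of arms.

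**The concern.** A covariate improves the precision of a rate comparison when it predicts the outcome. A between-arm baseline test says nothing about that. In a randomised trial it flags whichever variables happened to fall unevenly, and it does so equally often for useful and useless ones. The predictors the team itself singles out thus enter the primary model by luck, and unrelated variables enter by the same route.

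What is at stake is power on the primary comparison. Precision is expensive here: the amendment of 8/18/17 in Section G1 expected 10 extra subjects to need another 250 referrals.

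A second, separate gap concerns prespecification. The plan leaves open whether selected variables become covariates or propensity scores. It ties significance to the group term in a model with selected covariates, yet elsewhere describes Hypothesis 1 as unadjusted first and adjusted second. Two analysts could follow the plan and report different primary p values.

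**Working it through.** **The plan's own figures.** No power is stated for the primary comparison. The only power figures concern the executive dysfunction regressions (N = 100, alpha 0.05, two covariates): 97% at f² = 0.15 and 80% at f² = 0.08. A noncentral F test with 1 and 96 degrees of freedom and noncentrality f² × 100 gives 96.95% and 79.96%. They reproduce, but do not bear on this point.

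**Chance of omission (no assumption on strength).** Under randomisation, P(p<.25) is about 0.25 for any one baseline measure.
- One measure omitted: 1 − 0.25 = 75%.
- All three omitted, if independent: 0.75³ = 0.422, or 42% (44% at correlation 0.3).
- All three entered, if independent: 0.25³ = 0.016, or 1.6%.
- If each construct has two candidate measures, neither enters with probability 0.573 (correlation 0.3) to 0.625 (correlation 0.7).

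**Power, set-up A.** From the documents: 115 per arm, that is (220 + 10)/2, and 10% drop-out with partial exposure. Assumed: control rate 1 per year, dispersion 1, rate ratio 0.55, two-sided 5% Wald test, 15 candidate variables of which 3 are prognostic, and drop-out times uniform over the year. There were 4,000 simulated trials per row; power is in %, differences in points.

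| Rate multiplier per SD | Unadjusted | p<.25 rule | Three fixed | Fixed − rule | Fixed − unadjusted | Unadjusted − rule |
|---|---|---|---|---|---|---|
| 1.12 | 81.33 | 79.65 | 81.37 | 1.7 | 0.0 | 1.7 |
| 1.22 | 79.05 | 78.05 | 80.75 | 2.7 | 1.7 | 1.0 |
| 1.33 | 76.42 | 75.95 | 80.73 | 4.8 | 4.3 | 0.5 |

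The standard error of the fixed − rule column is 0.4 to 0.5 points. The last two columns separate the sources of loss. At 1.12 the predictors are worth almost nothing, and the loss comes from irrelevant covariates entering. At 1.33 nearly all of it comes from leaving the predictors out.

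Loss of the rule against the fixed set under other assumptions:
- Rate ratio 0.45: 0.7, 0.9 and 2.0 points for the three strengths. Rate ratio 0.70: 1.6, 2.9 and 3.6.
- 110 per arm, rate ratio 0.55: 1.7, 2.1 and 4.5.
- At 1.33 per SD, rate ratio 0.55: dispersion 2 or 4 gives 4.5 or 2.3; 8 or 25 candidates give 3.4 or 6.0; a control rate of 0.5 or 3 per year gives 3.7 or 2.9.
- A sparse case (0.3 per year, dispersion 4, 1.33 per SD): 1.5.
- Strong predictors (1.54 per SD): 8.4.

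**Power, set-up B.** 198 dyads (220 × 0.9), control rate 2 per year, dispersion 1.5, correlation 0.2, and only the three predictors as candidates. With yes/no predictors the losses are 0.7 (1.1 per SD), 1.1 (1.16), 3.0 (1.28), 5.3 (1.42), 7.2 (1.49) and 8.9 (1.65). Robust standard errors give 1.9, 4.4 and 10.6 at 1.16, 1.28 and 1.49. At 0.5 events per year the loss is about 0 to 1.6. The propensity-score version loses the same or up to about 1 point more.

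**In dyads (set-up A).** The variance of the log rate ratio is 4.1% to 13.2% higher under the rule than with the fixed set: 230 × 0.041 = 9 and 230 × 0.132 = 30 dyads.

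**Bias and type I error.** In set-up A, rejection under the null (unadjusted, rule, fixed) was 5.7, 5.3, 5.8% at 1.12 and 5.9, 5.1, 5.6% at 1.33 (standard error about 0.35). The mean estimated rate ratio was 0.545 to 0.549 for all three methods at a true 0.55. In set-up B the rule and the fixed set both rejected 5 to 7% of the time.

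**The case against.** The best defence is that the rule is written in advance and never looks at the outcome, so it does not steer the result. In set-up A it stays between 1.7 points below and 0.2 above no adjustment across nine combinations of effect and strength. In set-up B, with no irrelevant candidates, it gained up to 3.7 points over no adjustment. That defence stands against any charge of bias, but not against a comparison with fixed covariates.

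It is also fair that every driver of the power figure is assumed, including the 15 candidates. Few events are plausible, since Section F1 excludes anyone aggressive in the past month. This stands: the cost can be given only as a range that includes nearly zero.

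A construct may also get more than one chance to enter, because "Some of the questions asked at screening are also needed to characterize participants that enroll in the study" (Section F2). That lowers the omission rate per construct to about 57–62%. At 1.33 per SD in set-up A, the loss is then 3.9 to 4.1 points rather than 4.8.

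Three stronger readings are tempting:
- That the rule inflates type I error or biases the estimate. The checks above show no clear sign of either.
- That the plan states two conflicting selection rules. The Primary Hypothesis sentence, "Baseline demographic and clinical variables that differ between groups in univariate tests will be included as covariates or propensity scores", most naturally refers back to the p<.25 tests just described.
- That because Section C calls the predictors strong, the loss must be 7 to 11 points. Section C gives no effect per SD, so the word neither establishes that range nor rules it out.

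**Conclusion.** The concern holds as a matter of efficiency and prespecification. The rule covers the primary model, no section fixes the three named predictors for it, and the omission probabilities follow from randomisation alone (the 42% also needs independence).

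A reader might infer a firm loss of 1 to 5 points. The documents do not support a single figure. That range applies to predictors of roughly 1.15 to 1.4 per SD under the assumptions shown; the loss is near 0 with few events or very weak predictors and about 7 to 11 points with strong ones. In every setting tried, fixing the three scales either gained power or changed it by no more than simulation error. No loss is claimed for the Cox or mixed models.

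The open choice between covariates and propensity scores, and the unnamed deciding estimate, are gaps whatever the power figures turn out to be. The change is worth making because it is nearly free, not because the present rule would invalidate the result.

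**What to change.** In Section G1, for the primary model, delete the p<.25 selection and the propensity-score option. In their place:
- Specify a negative binomial model with treatment group, baseline pain (Philadelphia Geriatric Pain Intensity Scale), baseline depression (30-item Geriatric Depression Scale) and baseline relationship quality (Mutuality Scale), and log follow-up time as the offset, in all randomised dyads with follow-up.
- Before unblinding, name one score and one rater per scale. For pain, say whether the current or the past-week rating is used; for the Mutuality Scale, say whose rating counts. Give a simple rule for missing baseline scores.
- State that the chi-square for the group term in this adjusted model is the primary test, and that the unadjusted estimate is supportive.

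The cost is a change of wording and about three degrees of freedom. The outcomes concerned are already due for collection at baseline. If the scales prove barely prognostic (1.12 per SD), power in set-up A matched the unadjusted test within 0.4 points at all three rate ratios tried.

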In our prior and currently funded grants, we recruit patients using methods similar to those described in this proposal to identify PWD with clinically significant pain. To determine the number of patients available for this study, we asked our clinical partners to provide the number of PWD, using dementia ICD-IX codes and restricting to patients within 40 miles not living in a long-term care facility. We identified 1273 patients. Based on our prior studies, an estimated 60% of patients will meet the criterion for clinically significant pain, resulting in 764 existing eligible patients; broadening inclusion criteria to include pain-related features will result in even more eligible patients. On the basis of our prior recruitment data, we predict excluding approximately 30% of patients due to severe dementia, history of aggression, or lack of eligible caregiver. Thus, we estimate that 535 will meet all selection criteria. In our current APT study, we have had a consent rate of 80-90%. To conservatively estimate, an 80% consent rate results in 428 patients.

One-hundred consecutively enrolled subjects will be asked to do the CLOX Drawing Test at baseline to achieve our secondary objectives. This will give adequate power to detect significant differences of small to medium magnitude in outcomes between those with and without executive function (ED). Given an N of 100 and an alpha of 0.05, there is 97% power to detect a medium effect (F2 = 0.15) and 80% power to detect an effect size for ED (over and above two covariates) as small as F2 = 0.08.

Expected Recruitment Efforts and Minimization of Attrition. In our current VA Study and prior studies, we were able to enroll 6-8 dyads per month. In the VA study and others that we completed with PWD and their caregivers, attrition is about 10%; therefore, we plan to recruit 220 dyads, 6 patients per month over 37 months. We expect we will need to contact approximately 300 dyads using our partial HIPPA Waiver in order to enroll 220 dyads in the study.

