We have listed a sample size of 1500 above. This number is an estimate of the number of patient names/contact information we will receive from our partners (Baylor Geriatrics, Baylor Neurology, and Kelsey-Seybold) using our two recruitment methods: 1) database queries using our partial HIPPA Waiver and 2) direct provider referral. Many of these will turn out not to be eligible as described in the first paragraph of this section. See Sections J2 and F for details of our recruitment and screening methods.

Amendment 4/7/16: As of the end of March 2016, the percentage of patients referred from our clinical partners that have been enrolled in the study (assigned to APT or EU-PC) is less than expected (about 7%). Therefore, we are requesting to increase the number of patient names we will receive from our partners over the course of the recruitment period from 1500 to 2500. We still plan to randomize only 220 subjects.

Amendment 3/1/17: With pior IRB approval, we increased our sample size to 4000. This is the number of database and direct referrals we anticipated we would need in order to enroll 220 subjects based on the percent of referrals enrolled over the course of the study (less than 7%).

Amendment 8/18/17: With IRB approval, we will enroll and extra 10 subjects to replace someof our drop-outs. In order to do this we expect to need another 250 referrals (database and direct) from our clinical partners. Therefore the sample size above has been increased to 4250.

Provide a description of your plan for data analysis. State the types of comparisons you plan (e.g. comparison of means, comparison of proportions, regressions, analysis of variance). Which is the PRIMARY comparison/analysis? How will the analyses proposed relate to the primary purposes of your study?

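### In the primary model, a drop-out's time counts up to attrition but aggression after the last interview can go unrecorded, and no sensitivity analysis tests what this does to the result

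*Combined protocol and SAP*

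**What the plan says.** All references are to the combined protocol and SAP.

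- **Section G, Primary Hypothesis.** The model: "We will use negative binomial regression models to estimate the difference between our intervention and the control group in the rate of aggressive behavior". The rule for drop-outs: "For participants who drop out of the study, their time until study attrition will be used as their exposure period". This rule fixes the exposure time. It says nothing about the event count.
- **Section F2, Assessments.** Outcomes are collected at baseline and at 3, 6 and 12 months. Apart from the clock-drawing test, "The remainder of the assessments will be administered by telephone". No assessment at withdrawal is described.
- **Section C.** Of aggressive behaviors the protocol says that "they lead to increased institutionalization, injuries, caregiver burden and use of antipsychotic medications".
- **Section G, Attrition Rates and Missing Data.** "In general, the primary source of missing data will be through participant attrition", and "We anticipate a low attrition rate (10%) based on our prior work". The safeguards listed are a chi-square comparison of attrition between arms, secondary-source information to see whether drop-outs differ from other participants, multiple imputation for missing items, and hierarchical linear models.
- **Section G, Secondary Hypotheses 1.** Nursing-home admission is a followed outcome with its own Cox model.
- **Section G1.** "therefore, we plan to recruit 220 dyads, 6 patients per month over 37 months". The amendment of 8/18/17 adds: "we will enroll and extra 10 subjects to replace someof our drop-outs".

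**The concern.** A negative binomial model with exposure running to attrition treats leaving the study as unrelated to aggression. The protocol's own premise makes that doubtful: if aggression raises caregiver burden and institutionalization, some dyads may leave because of it. When that happens between interviews, the time up to exit enters the denominator and the event that caused the exit does not enter the numerator.

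The listed safeguards do not reach this. Imputation is for missing items. Hierarchical models belong to the secondary outcomes, and the plan describes them as handling missing observations other than attrition. The chi-square test compares how many left, not why. The secondary-source information is not stated to enter the primary count. Replacing drop-outs restores numbers but not lost events.

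The only primary hypothesis rests on this ratio. APT aims to change burden and caregiver skills, so the chance that an aggressive episode ends in withdrawal could plausibly differ by arm, in either direction.

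**Working it through.** **Inputs from the documents.** 220 dyads, 1:1 allocation, 10% attrition, interviews at 3, 6 and 12 months. Expected drop-outs: 220 × 0.10 = 22, or 11 per arm if balanced. The longest unobserved gap is 12 − 6 = 6 months. No aggression rate, effect size or power is stated for the primary comparison, so there is no plan figure to reproduce.

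**Assumptions, not from the documents.** One-year onset of 40% in EU-PC and 25% in APT at constant hazard. A fraction *q* of onsets leaves at a random time between onset and the next interview. Background drop-out brings each arm to about 10%. Exposure runs to attrition. An onset is recorded only if the next interview is completed, and that interview is assumed to capture everything since the previous one.

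**Step 1: what each *q* implies.** Share of an arm's drop-outs that is aggression-driven = onset × *q* / attrition.

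- EU-PC, *q* = 12.5%: 0.40 × 0.125 / 0.10 = 50%
- EU-PC, *q* = 25%: 0.40 × 0.25 / 0.10 = 100%
- EU-PC, *q* = 10%: 0.40 × 0.10 / 0.10 = 40%
- APT, *q* = 6%: 0.25 × 0.06 / 0.10 = 15%
- APT, *q* = 10%: 0.25 × 0.10 / 0.10 = 25%
- APT, *q* = 25%: 0.25 × 0.25 / 0.10 = 62.5%

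**Step 2: simulated rate ratio, APT to EU-PC** (recorded onsets divided by exposure, large samples). The complete-data ratio is 0.25 / 0.40 = 0.625.

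| *q* EU-PC, APT | Aggression-driven share of drop-outs | Rate ratio |
|---|---|---|
| 0, 0 | none | 0.62 |
| 25%, 25% | 100%, 62.5% | 0.61 |
| 12.5%, 6% | 50%, 15% | about 0.66 |
| 25%, 10% | 100%, 25% | 0.71 to 0.72 |
| 25%, 0 | 100%, 0 | 0.78 |
| 10%, 25% | 40%, 62.5% | 0.53 |

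In the second row the ratio is nearly unchanged, but recorded incidence falls to 30% (0.40 × 0.75) and 18%. Attrition is 10% in both arms in every row, so the planned chi-square test would have nothing to detect.

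**Step 3: the same question with event counts.** Here the negative binomial model with a log-exposure offset was simulated, assuming a control rate of 1 event per person-year, gamma frailty with shape 1 and dispersion fixed at 1.

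- Unrelated drop-out near 10%: true ratios of 1.0 and 0.5 are recovered as 1.00 and 0.50.
- Same aggression-driven mechanism in both arms: each arm's rate is understated by about 8 to 15%; true ratios of 1.0, 0.7 and 0.5 stay at about 1.00, 0.70 and 0.50.
- A 16% against 5% chance of leaving after an event: a true ratio of 1.0 becomes 1.14 or 0.88, depending on which arm has the higher chance.
- Type I error at 110 per arm: about 5% with unrelated drop-out, about 6% with a common mechanism, about 10.5% with 16% (EU-PC) against 5% (APT).

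**Step 4: would a shorter exposure repair it?** Ending exposure at the last completed interview moves 0.712 to 0.708 and 0.783 to 0.776 in the onset model, and 1.14 to 1.12 in the count model. The missing events cause the bias, not the extra time.

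**The case against.** The strongest reply is that the gap is narrow and that the plan is easily read as worse than it is.

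- A reader might infer that drop-outs are entered as aggression-free. The text does not say so. It sets exposure only, and aggression recorded before exit counts. Only unrecorded aggression after the last interview is affected. This stands.
- A reader might infer that nursing-home placement ends follow-up, so that the most aggressive participants are lost. No section says so. Living outside a nursing home is an entry criterion, placement is a followed outcome, and telephone interviews could continue. This also stands, but no section says that interviews do continue, and withdrawal because of caregiver burden needs no placement.
- Bias in the ratio needs a mechanism that differs by arm, and the documents show none. This is correct. The two arms do differ in caregiver contact (home skills sessions against 15-minute calls), which makes a difference plausible but not established.
- The larger shifts need extreme inputs. Step 1 confirms it: every row with 25% in EU-PC makes essentially all EU-PC drop-outs aggression-driven.
- The onset simulation is not the planned count model. The count version in Step 3 leads to the same conclusion.
- The plan does address attrition, through the arm comparison and the secondary sources. Both deserve credit, but neither is stated to alter or test the primary estimate.

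**Conclusion.** The point holds as a conditional one. The primary analysis can count time without the aggression that ended it, and the plan has no analysis showing whether this matters. The documents do not support saying that the arm comparison is biased, nor in which direction.

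The size depends on assumed rates. With a common mechanism, the loss is in recorded incidence and power. With a moderate difference between arms, the ratio moves from 0.62 to about 0.66. Shifts to 0.71 to 0.78 require nearly all EU-PC drop-outs to be aggression-driven, and the reverse pattern gives 0.53. At the planned attrition, about 11 dyads per arm can hide an event. If actual attrition exceeds 10%, the possible shift grows. This is worth correcting because it touches the only primary hypothesis and the remedy is cheap.

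**What to change.** 1. State that nursing-home placement does not end outcome collection and that caregiver telephone interviews continue to 12 months.
2. At any withdrawal, ask the caregiver for the reason and whether aggression occurred since the last interview; failing that, use the secondary source already planned. Say that the answer enters the primary count.
3. Add a tipping-point analysis over drop-outs still without exit information. Add a version that counts placement or behavior-related withdrawal since the last interview as aggression in both arms.
4. Where no exit information exists, ending exposure at the last completed assessment aligns events with time at risk. It should not be presented as a cure (Step 4).

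The cost is SAP wording, one exit question for about 22 dyads and two extra analyses. Some placements have other causes and would be misclassified, so that rule belongs in the sensitivity analysis only. If exit information can no longer be collected, the tipping-point analysis can still be run.
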